10. OUTCOME MEASURES

10.1 Primary outcome measure

The primary outcome measure of the IPPOMS is the rate of disability progression, assessed with the Area Under the Curve (AUC) of the CombiWISE scores during the 2-year treatment period. The CombiWISE data collected during the 1-year pre-treatment period will be utilized by including both the pre-treatment disability progression (AUC of CombiWISE scores during the pre-treatment period) and severity of the disability (CombiWISE score at pre-randomization baseline) as covariates in the statistical analysis.

CombiWISE was developed based on the pre-determined analysis of 58 candidate outcomes collected in 1 year pre-treatment phase in 1 training (IPPOMS1) and 2 validation (IPPOMS2 and RIVITALISE) cohorts, as described in detail in recent publication (Kosa, Ghazali et al. 2016). CombiWISE is a continuous scale ranging from 0 to 100, has strong correlation with EDSS (i.e., scale used for regulatory approval of MS drugs; $\rho = 0.9805$, $p < 0.0001$, $n = 303$) and has the strongest power among all 58 tested outcomes (Kosa, Ghazali et al. 2016).

10.2 Secondary outcome measures

10.2.1 Neuroimaging outcomes

1. Inhibition of individualized rates of enlargement of ventricular volume: effect of idebenone versus placebo on individualized rates of enlargement of segmented volume of lateral and 3rd ventricles

10.2.2 Clinical/functional outcomes

1. Progression in EDSS-plus, as defined in (Cadavid, Cohen et al. 2017). EDSS-plus response will be analyzed using a cox proportional hazards model.
2. Progression of lower extremity disability as assessed by 25 foot walk component of MSFC
3. Progression of upper extremity/fine motor movements disability as assessed by non-dominant hand 9 hole peg test component of MSFC
4. Progression of neurological disability as assessed by Scripps NRS
5. Progression of neurological disability as assessed by EDSS

10.3 Exploratory outcome measures

10.3.1. Neuroimaging

1. Progression of retinal nerve fiber thinning as detected by OCT (comparing idebenone to placebo)

10.3.2. Clinical

1. Progression in cognitive dysfunction as assessed by Symbol Digit Modality Test (comparing Idebenone to placebo)
2. Progression of neurological disability as assessed by MSFC

10.3.3. Biological/immunological

1. Analysis of changes in CSF albumin quotient between idebenone and placebo (ROS are known to disrupt endothelial tight junctions; which may be measured as increase in CSF albumin quotient)
2. Analysis of changes in CSF biomarkers of activated/pro-inflammatory microglia/monocytes (sCD14)
3. Analysis of changes in CSF lactate/pyruvate ratio, as a biomarker of extra-mitochondrial glucose metabolism
4. Analysis of changes in CSF growth differentiation factor 15 (GDF15), as a putative biomarker of mitochondrial dysfunction
5. Analysis of changes in CSF neurofilament light chain (NF-L), a biomarker of axonal damage

11. STATISTICAL ANALYSIS

11.1 *Data acquisition and processing*

All clinical, neuroimaging volumetric and biomarker data will be collected sequentially and analyzed in a blinded fashion from coded samples. Data will be acquired prospectively and transcribed to the research database. For the imaging biomarker of ventricular volume the analysis will be performed only after completion of baseline or treatment periods, because the images need to be co-registered to the first acquired image. For biomarker data that can be acquired from cryopreserved biological samples, baseline and treatment data points will be evaluated simultaneously, to limit effect of inter-assay variation. Every effort will be made to have single rater/investigator to acquire one type of quantifiable clinical, neuroimaging and biomarker data for the entire cohort. Codes will be broken only after all pre-specified quantifiable data constituting primary and secondary outcomes are collected and recorded in the database.

11.2 *Statistical analyses of outcome measures*

Further details of the statistical analysis (e.g. definition of analysis populations) will be defined in a Statistical Analysis Plan which will be finalized before the database lock and opening of the treatment code.

Introduction

- a) For data collected only at 2 time-points (i.e. single collection during pre-treatment baseline and single collection at 1 year of therapy), such as CSF data, we will calculate for each individual %-change between baseline and therapy time-points
- b) For data collected every 6 months (i.e. clinical data and quantitative brain MRI data) we will calculate area under curve (AUC) for 3 data points obtained during pre-treatment baseline period and compare it to AUC for 5 data points obtained during the treatment period.

The rationale for using AUC (as opposed to linear regressions) is explained in detail in Figure 3:

[figure not shown]

Figure 3: There are two possible ways how changes in outcomes collected every 6 months (e.g., primary outcome: CombiWISE) can be analyzed: 1. As a change in regression slopes (left panel) or 2. As a change in AUC (right panel). There are two major problems with regression slopes: First, the baseline pre-treatment period slope is derived only from 3 measurements. Because these measurements are spread equally apart, the least squares linear regression slopes are calculated only from 1st and 3rd measurement, whereas the middle (2nd) measurement affects only the intercept. Consequently, even though we have three baseline measurements, only two of them would be de-facto utilized for final outcome comparison. Furthermore, as depicted in the left panel, if the drug has both neuroprotective effect (which decreases slope) and promotes structural or functional repair (which decreases intercept), comparing slopes would de-facto ignore the latter potentially important mechanism of action (MOA). In contrast, measuring changes in disability progression between untreated and treated period using AUC (right panel) eliminates both stated disadvantages of progression slopes. This method uses all measured data and correctly deals with the improvements in disability by subtracting parts of the curve that are below the baseline (i.e. CombiWISE measure at the initiation of therapy) from the AUC part that is above the baseline.

The only problem with AUC is unequal length of the compared periods: while pre-treatment baseline period has 1-year length, the treatment period for IPPOMS trial has length of 2 years. It may be intuitive to divide 2-year AUC period by 2 to obtain equivalent yearly measurements, but that is incorrect. As depicted in the left panel, if the progression slopes were linear, the AUC derived from 2-year period needs to be divided by 4 to get equivalent yearly AUC progression. We have validated correctness of this adjustment by analyzing blinded 2 year CombiWISE data from 50 patients who finished 2 years of study and by comparing average AUC derived from splitting Year 1 and Year 2 of this longitudinal cohort, versus calculating AUC from the entire 2-year period. We observed that these two measurements strongly correlate with each other ($r^2=0.905$) with following linear regression formula:

$$Y = -0.77 + 3.96 * X, \text{ where } X \text{ is average yearly AUC and } Y \text{ is 2-year AUC measured in the same patient.}$$

Consequently, this mathematical analysis confirmed that 2-year AUC must be divided by 4 to obtain equivalent yearly change. The intercept (-0.77) represents improvement in disability, which is incorrectly ignored when the treatment period is split into two yearly AUCs.

Statistical Hypothesis

The hypothesis to be tested for the primary efficacy endpoint CombiWISE is:

H₀: There is no difference between idebenone and placebo in the disability progression during the 2-year treatment period.

The alternative superiority hypothesis is

H_A: The disability progression in idebenone-treated patients is slower than in the placebo-treated patients during the 2-year treatment period.

In addition to the difference between the treatment groups, the within-group changes in each treatment group will be evaluated by comparing the disability progression during the pre-treatment period to the progression during the treatment period.

The analysis for the primary outcome measure CombiWISE will be performed in all randomized patients using a two-sided type I error rate of $\alpha = 0.05$.

Primary Analysis of the Primary Outcome Measure

The AUCs of the CombiWISE scores during the 2-year treatment period will be analyzed using an Analysis of Covariance (ANCOVA) model with the AUC of the pre-treatment CombiWISE scores, Baseline (Month 0) CombiWISE score and Baseline age as covariates.

The incomplete data in the CombiWISE scores during the 2-year treatment period will be managed with the single imputation algorithm defined in Section 5.3.

The within group changes will be tested using paired t-test within each treatment group. For this analysis, to compare the 1-year pre-treatment period changes to 2-year treatment period changes, the treatment period AUC values will be divided by 4.

Sensitivity Analyses of the Primary Outcome Measure

1. Random coefficient regression model with random intercept and slope will be fitted to the response data. All CombiWISE scores will be included as response variables in the model. In order to model random intercept and slope for pre-and post-treatment separately, factor period (pre vs. post) will be created: pre -treatment (Month -12 to 0) vs. post-treatment (Month 0 (+1 day) to 24). Exact days from the first visit, instead of month will be used as Time in the model. In addition to the random slopes and intercepts, the model will include the fixed effect for treatment group (idebenone or placebo), period (nested within treatment), interaction between Time and period (nested in treatment) and covariates: Baseline (Month 0) CombiWISE score and Baseline age. The interaction between Time and period (nested within treatment) will be used to examine the hypothesis of four slopes are same (slopes for placebo group at pre- and post-treatment, slopes for idebenone group at period pre-and post-treatment). The pairwise comparisons of the four slopes or intercepts,

such as slope (or intercept) at post-treatment for idebenone group vs. that for placebo group, and slope (or intercept) for idebenone group at post-treatment vs. that at pre-treatment period can be constructed and performed using the statement “estimate”. This analysis includes only the observed CombiWISE scores as response variables and as the model can manage incomplete data, no imputation will be done.

2. Mixed Model for Repeated Measures (MMRM) will be fitted to the response data. The observed CombiWISE scores from all scheduled post-baseline visits (Month 6, 12, 18 and 24) will be used as response variables in the model. The model will include visit, treatment group (idebenone or placebo) and the interaction between visit and treatment group as fixed factors. The Baseline (Month 0) CombiWISE score, baseline age and the rate of decline in the CombiWISE scores during the pre-treatment period will be used as covariates in the model. Both the overall treatment difference at all visits (Months 6, 12, 18 and 24 post-randomization) and the treatment difference separately at each visit will be estimated from the model. The overall treatment difference will be tested based on the fixed factor for the treatment group and the visit-specific treatment differences will be tested with contrasts derived from the fixed factor for treatment group and the interaction term between visit and treatment group. The focus of this analysis will be on the early treatment difference observed at Month 6 post-randomization and the treatment difference at the last study visit (Month 24 post-randomization). An unstructured covariance structure will be applied for the MMRM. The denominator degrees of freedom will be computed using the Kenward-Roger method. The covariate for the rate of decline will be calculated separately for each subject from the CombiWISE scores observed during the pre-treatment period using a random coefficient regression model with random intercept, random slope and time (exact number of days since the first assessment) as an explanatory factor.
3. Multiple Imputation (MI) assuming data missing at random (MAR) will be done to compare idebenone to placebo. MI techniques based on Pattern Mixture Models (PMM) will be applied in this sensitivity analysis. This methodology will structure data based on the missing data patterns. The method will be based on a missingness pattern having a monotone structure, i.e. if among the observations during the 2-year treatment period one CombiWISE score is missing, all subsequent scores after this missing value will also be treated as missing. For patients with intermittent missing values, before performing MI based on the PMM, it will be necessary to create a monotone missingness pattern. Intermittent missing values will be imputed using the Markov Chain Monte Carlo (MCMC) methodology which assumes a multivariate normal distribution over all variables included in the imputation model. This first MI step is planned to be repeated 1000 times, creating 1000 different datasets with a monotone missing data structure. Seed value of 1995 will be used in the MI procedure. The imputation is based on the missing at random (MAR) assumption, i.e. the missing data are assumed to follow the same model as the other patients in their respective treatment arm.

After this, the remaining missing data will be imputed using a method for monotone missingness, also based on the MAR assumption. Thus, for each of the 1000 created dataset with a monotone missing data pattern, missing values will be imputed based on a sequential procedure reflecting the monotone missing data pattern. Patients with the first missing value occurring at Month 3 will have their missing Month 3 value replaced by an imputed value from a regression model with treatment group, Month 0 CombiWISE score, the pre-

treatment slope and baseline age as explanatory variables. In the next step, patients with their Month 6 value missing will have their missing Month 6 value replaced by an imputed value from a regression model with all factors defined above and Month 3 value as explanatory variables. Similar procedure will be used to replace the missing values at all subsequent visits.

The imputed datasets generated with the approach described above do contain only non-missing values and are used as input in the model for the sensitivity analysis of the primary outcome variable. MMRM similar as described in Sensitivity Analysis 2 will thus be run on each of the 1000 generated imputed datasets and the difference between the treatment groups will be estimated. Finally, the results from these analyses will be combined to derive an overall estimate of the treatment difference. In addition to the estimates, corresponding 95% confidence intervals and p-values will be calculated.

4. Multiple Imputation assuming data missing not at random (MNAR) will be done to compare idebenone to placebo. Control group based assumption (Copy Reference imputation) will be used, i.e. the trajectories of the patients are assumed to follow the placebo group trajectories after the discontinuation. Methods similar to the procedure described above will be used to generate monotone missing data. After this, the missing data will be imputed sequentially for each visit (first Month 3, followed by all subsequent visits). Only the data from the control group (placebo group) will be used as input for each imputation of both treatment groups.

Secondary Endpoints

Continuous variables will be analyzed using random coefficient regression models and/or MMRMs similar to the one defined above for the primary outcome variable

Categorical Endpoints will be analyzed using cox proportional hazards models, with treatment group, baseline values (if applicable) and baseline age as covariates.

11.3 Handling of missing/unobtainable data

All efforts will be made to collect a complete set of data by employing 1-2 week flexibility in scheduling and repeating inadequate quality MRI scans.

With the exception of the primary endpoint (AUCs) and the sensitivity analyses, for continuous and categorical endpoints, no data imputation will be made and missing data will be handled by the models itself.

The following single imputation method is applicable for handling of missing data to calculate AUCs of CombiWISE scores and MRI data.

If particular data points are missing for reasons other than inability to perform the test (i.e. because of disability) we will replace the missing data according to following algorithm:

- a. For data obtained every 6 months (i.e. clinical data and brain MRI data), the missing time point will be substituted by the average of 2 adjacent time-points: i.e. 6 months before and 6 months after the missing time-point. If the last time-point is missing (i.e. month 24), we will substitute the data for this time-point by the average of 2 preceding time-points.
- b. For data obtained once at baseline and once at treatment phase (i.e. CSF), the missing data cannot be replaced and the patient will be eliminated from analysis.

Handling data missing because the patient was unable to perform the test due to disability: this may happen for clinical tests such as timed 25 foot walk (25FW), 9 hole peg test (9HPT) and PASAT. These data will be calculated using the following recommendations from scoring instructions for the MSFC:

- a. 25FW: the inability to perform 25FW will be substituted by the largest Z-score in the MSFC Task force database (i.e. with the slowest time of any patient in the combined dataset used by the Task Force in its published meta-analysis). The largest Z-score in the Task Force dataset is 13.7, therefore, for a subject who could not complete the 25FW $Z_{leg, average} = -13.7$ will be used.
- b. 9HPT: the inability to perform 9HPT will be coded as 777 and the following Z-score calculation formula will be applied:

$$Z_{arm, trial\#} = [(1/777 - \text{Baseline mean (1/9HPT)}) / \text{Baseline SD (1/9HPT)}]$$
- c. PASAT: In the event an individual patient cannot complete PASAT-3 due to disability, a score of 0 will be assigned.

For missing data for CombiWISE calculation, the CombiWISE formula (Kosa, Ghazali et al. 2016) specifies handling of the inability to perform either 25FW or non-dominant hand 9HPT as a separate variable.

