This analysis was performed and published, including measurements of z-scores (*Kosa, Ghazali et al. 2016*). We have compared total of 58 clinical, imaging, electrophysiological and optical coherence tomography outcomes. In the first IPPOMS cohort (which ended up being 35 patients because we lost some MRI outcomes due to technical issues such as poor quality of scans and the protocol stipulated minimum of 30 patients per outcome) we observed that total of 15 outcomes reached statistical significance based on un-adjusted p-values (See Table 2 in the (*Kosa, Ghazali et al. 2016*)). We then validated these 15 outcomes for their ability to reliably detect yearly MS disease progression in 2 independent validation cohorts: IPPOMS2 cohort (n=34) and RIVITALISE cohort (n=29). Seven out of 15 outcomes validated statistically-significant change in both independent validation cohorts, when properly adjusting for multiple comparisons. Surprisingly, the default primary outcome for IPPOMS protocol, brain atrophy measured by SIENA methodology was not validated. While six MRI biomarkers (ventricular volume and 5 diffusion-tensor imaging [DTI] markers) validated statistically-significant change in both validation cohorts, our enthusiasm for these outcomes was lowered by observation that only one of them, ventricular atrophy, showed any correlation with clinical outcomes. This measure had mild correlation with 2 cognitive scales (PASAT and SDMT) and with a MS functional composite (MSFC) scale. However, this correlation was observed only in the cross-sectional paradigm, which benefited from a broad range of disabilities present in merged untreated progressive MS cohort (n=98). In contrast, we observed absolutely no correlation between any MRI outcome and any clinical measure in 1-year longitudinal paradigm – in other words, change on MRI biomarkers did not correlate with change in any clinical outcome. The article explains in length why this is so, documenting poor signal-to-noise ratio (SNR) of even best performing MRI biomarkers for the level of change observed in the 1-year longitudinal MS data in comparison to scan-re-scan variability observed in MRI technical controls (i.e. healthy donors scanned twice at each scanner).

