The AUC values will be calculated for both the pre-treatment baseline phase (from Months -12, -6 and 0) and for the double-blind phase (from Months 0, 6, 12, 18 and 24). For each of the AUC values, at least two valid CombiWISE scores during the phase in question are required. If less than two values AUC values are available for any of the two phases, the AUC score will be set as missing. In addition, if the first value of the phase in question is missing, the CombiWISE score will be set as missing.

Linear trapezoidal method will be used to calculate the AUC values. For each time interval (time between two visits), the AUC is calculated as $0.5 \times (Y_1 + Y_2) \times (t_2 - t_1)$, where Y_1 and Y_2 are the CombiWISE scores (as changes from baseline) at the beginning and end of the interval and t_1 and t_2 are the start and stop dates of the interval. The time will be converted to years (number of days divided by 365.25) for the AUC calculation. The baseline for the pre-treatment period is the visit scheduled at the beginning of the pre-treatment period (Month -12) and the baseline for the double-blind period is the visit at Month 0.

In case of intermittent missing data between two non-missing visits, the formula for linear trapezoidal method will be used as such. In case of premature discontinuations, the AUC values after the time of discontinuation will be set as missing.

After these calculations, the AUC values calculated for the different periods will be summed over the pre-treatment baseline phase (Month -12 to Month 0) and over the double-blind phase (Month 0 to Month 24). Because the follow-up times can vary from patient to patient, the AUC values will be made comparable by scaling them using the follow-up time. The scaling will be done by dividing the AUC value by the square of the actual duration of each of the phases. For the pre-treatment baseline phase, the AUC will be scaled as $AUC/[t_0 - t_{-12}]^2$, where t_0 and t_{-12} are the dates of visits at Month 0 and Month -12, respectively. For the double-blind phase, the AUC will be scaled as $AUC/[t_{last} - t_0]^2$, where t_{last} and t_0 are the dates of the last visit and the visit at Month 0, respectively. Similarly as above, the time will be converted to years. The scaled AUCs will be used in all statistical analyses.

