13.1 Primary endpoint: AUCs of CombiWISE scores

13.1.1 Primary analysis

The AUCs of the CombiWISE scores will be analyzed using an Analysis of Covariance (ANCOVA) model with the AUC of the pre-treatment CombiWISE scores, Baseline (Month 0) CombiWISE score and Baseline (Month 0) age as covariates.

The incomplete data in the CombiWISE scores during the 2-year treatment period will be managed with the single imputation algorithm defined in Section 4.2.

In addition to the primary analysis comparing the between-group difference, the within group changes will be tested using paired t-test within each treatment group. The t-tests will be based on Satterthwaite's approximation.

The analyses will be conducted both using the ITT population (primary) and Completer population (secondary).

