13.2 Secondary Endpoints

Continuous secondary endpoints (other than the neuroimaging outcomes) will be analyzed using random coefficient regression models similar to the one defined above for the primary outcome variable. In addition, analyses using MMRM will be conducted as well, in order to estimate the treatment differences separately at each visit. The neuroimaging outcomes will be analyzed by calculating AUC values and using ANCOVA models, similar to the primary analysis.

Categorical time-to-event endpoints (EDSS-plus) will be analyzed using Cox Proportional hazards models, with treatment group as a covariate. The patients who do not have an event during the study will be censored at the time of the last assessment of EDSS-plus. The exact number of days from the date of first dose to date of event or censoring will be used as endpoint.

The ITT population will be used for the analysis of the secondary endpoints.

14 Analysis of safety

The safety analyses will be conducted for the following study periods and treatment groups:

- Pre-treatment baseline phase: untreated patients, classified by the treatment group in the double-blind phase and overall
- Double-blind phase: Idebenone treated patients versus placebo treated patients

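### For the ventricular-volume AUC, the plan does not rule out filling a missing Month 0 scan from the on-treatment Month 6 scan

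*Protocol*

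**What the plan says.** Protocol 11.3 introduces its rule with "The following single imputation method is applicable for handling of missing data to calculate AUCs of CombiWISE scores and MRI data". For data collected every 6 months, "the missing time point will be substituted by the average of 2 adjacent time-points: i.e. 6 months before and 6 months after" the gap. Month 24 has its own rule. Month 0 is not mentioned, and nothing bars averaging across randomisation.

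SAP 4.2 treats CombiWISE differently. It fixes the origin of the treatment-period AUC: "the baseline for the double-blind period is the visit at Month 0". It then says that "if the first value of the phase in question is missing, the CombiWISE score will be set as missing". Gaps inside a phase are bridged rather than filled: "In case of intermittent missing data between two non-missing visits, the formula for linear trapezoidal method will be used as such". SAP 13.1.1 sends the primary ANCOVA to these rules, saying that incomplete data "will be managed with the single imputation algorithm defined in Section 4.2". The SAP's introduction states that it takes precedence where it differs from the protocol.

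For ventricular volume, a secondary endpoint, SAP 13.2 gives one sentence: "The neuroimaging outcomes will be analyzed by calculating AUC values and using ANCOVA models, similar to the primary analysis". It states no missing-data rule of its own. SAP 16 lists the AUC scaling as the change to the primary analysis and does not mention any change to the missing-data rule.

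**The concern.** Month 0 does several jobs. It closes the pre-treatment AUC and is the zero point of the treatment AUC. If the MRI analysis mirrors the primary one, it is also an ANCOVA covariate in its own right. Filling it partly from Month 6 puts a post-randomisation measurement, which treatment may have changed, into the baseline and the covariates. If the drug works by Month 6, half of that early effect is absorbed into the baseline of the treated patient and then subtracted from every later visit.

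Missing scans are a realistic possibility. Protocol 11.5 reports of the outcome-selection cohort that "we lost some MRI outcomes due to technical issues such as poor quality of scans". At stake is a diluted estimate for ventricular volume, and an analysis rule that two programmers could implement differently.

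**Working it through.** **Which rule applies**

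| Endpoint | Protocol 11.3 | SAP | Result if Month 0 is missing |
|---|---|---|---|
| CombiWISE AUC | Neighbour average | 4.2, by name: set to missing | Not filled from Month 6 |
| Ventricular-volume AUC | Neighbour average, MRI named | 13.2: like the primary analysis | Not settled |

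SAP 4.2 speaks of the score where the AUC is probably meant. On either reading Month 6 does not enter the CombiWISE baseline.

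**Plan's own figures.** The documents give no figure for missing Month 0 values. The CombiWISE power table in SAP 6.2 reproduces in all seven rows (for example 28 pairs, power 0.807, at a 50% effect), but it concerns an endpoint that this point does not touch.

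**Inputs for the size of the effect.** Visits at 0, 0.5, 1, 1.5 and 2 years; linear trapezoid on change from Month 0 (SAP 4.2). Trapezoid weights are 0.25, 0.5, 0.5, 0.5, 0.25. Assumptions: progression is linear at b per year in untreated and placebo patients, there is no placebo response, and true Month 0 is set to 0.

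**General formula.** If Month 0 is replaced by f, the change at Month 0 is still zero and every later change shifts by -f. The later weights sum to 0.5 + 0.5 + 0.5 + 0.25 = 1.75, so

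AUC(filled) = AUC(true) - 1.75 f.

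**Placebo.** f = (-0.5b + 0.5b)/2 = 0. The AUC stays at 2.00b.

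**Idebenone, slope slowed by 50%.**
- Month 6 value: 0.5 × 0.5b = 0.25b.
- f = (-0.5b + 0.25b)/2 = -0.125b.
- True AUC: 1.00b. Filled AUC: 1.00b + 1.75 × 0.125b = 1.219b.
- Difference from placebo: 2.00b - 1.219b = 0.781b instead of 1.00b, a loss of 21.9%.
- After SAP scaling (division by 2² = 4): 0.195b instead of 0.250b.
- The pre-treatment AUC also moves, by 0.25 × (-0.125b), from 0.500b to 0.469b.

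For any fractional slowing e, f = -0.25eb, the shift is 0.4375eb and the true effect is 2eb. The proportion lost is 0.4375/2 = 21.9% whatever e is.

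**Idebenone, immediate step effect d.** The true AUC effect is 1.75d. f = -d/2, so the shift is 0.875d and the remaining effect is 0.875d, a loss of 50%.

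**Delayed effect, none at Month 6.** f = 0 and nothing is lost.

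**Arm level.** Loss = per-patient loss × share of idebenone patients missing Month 0. The share is assumed:

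| Share missing Month 0 | 50% slowing (0.219 × share) | Step effect (0.5 × share) |
|---|---|---|
| 5% | 1.1% | 2.5% |
| 10% | 2.2% | 5% |
| 20% | 4.4% | 10% |

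**No drug effect.** The fill then behaves alike in both arms, so it creates no between-arm bias.

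These figures are for the unadjusted AUC. The ANCOVA estimate, with its altered covariates, was not computed.

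**The case against.** The strongest reply is that the SAP governs and has only one AUC calculation, in Section 4.2, so a neuroimaging analysis modelled on the primary one would naturally inherit the first-value rule. That is probably the intended reading. It remains an inference: the sentence names CombiWISE, whereas Protocol 11.3 names MRI data. SAP 13.1.1 also calls Section 4.2 a single imputation algorithm although 4.2 fills no visit value, so a programmer looking for such an algorithm would find it only in Protocol 11.3.

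Protocol 11.3 is itself unclear. Just before the averaging rule it limits imputation to the primary AUC endpoint and the sensitivity analyses, which would leave out a secondary MRI endpoint; the next sentence then brings MRI back in. This supports calling the rule unresolved rather than wrong.

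The frequency may be very low. Protocol 11.3 commits to repeating inadequate scans, and Protocol 7.4 has patients complete the baseline period before randomisation. A reader might take a rate from Protocol 11.5, where 35 patients were used against a minimum of 30 per outcome. That passage concerns unspecified MRI outcomes among 58 candidates and gives no rate for ventricular volume at Month 0.

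A reader might also infer that the primary baseline is contaminated, or that this explains the negative result reported in Protocol 7.6. Neither is supported: SAP 4.2 keeps Month 6 out of the CombiWISE baseline, and the plausible loss for ventricular volume is a few percent.

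**Conclusion.** The point holds for the ventricular-volume AUC only, as an unresolved rule with a small possible consequence. The primary analysis is unaffected. If Protocol 11.3 is applied to MRI, an affected idebenone patient loses about 22% of the unadjusted AUC effect under proportional slowing and 50% under an immediate step; a delayed effect loses nothing. Arm-level dilution is 1.1-4.4% at an assumed 5-20% missing with 50% slowing. The true share is not in the documents.

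It would go too far to say that the distortion falls in the idebenone arm alone. That requires linear progression and no placebo response; with curvature or a placebo response, the placebo fill is off as well. Type I error is not inflated by this route. Severity is minor: one secondary endpoint, in a study whose SAP describes it as exploratory and makes no multiplicity adjustment for secondary endpoints.

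**What to change.** State in Protocol 11.3 and SAP 13.2 that a missing Month 0 value is never replaced using a post-randomisation value. For ventricular volume, apply the first-value rule of SAP 4.2, so that the treatment-period AUC is missing. As a sensitivity analysis that keeps the patient in the ANCOVA, predict Month 0 from pre-randomisation data with one model for both arms. Leave the CombiWISE rule in SAP 4.2 as it is. List the departure from Protocol 11.3 in SAP 16.

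Protocol 7.6 says that the analysis is complete, so the practical step is to report the number of missing Month 0 values by arm and endpoint and which rule was used, and to rerun ventricular volume if any Month 0 scan was filled from Month 6.

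The cost is a few sentences and either a few lost patients or a noisier baseline for them. The noise is not trivial. With independent measurement error of variance σ², straight-line extrapolation (2 × Month -6 minus Month -12) has error variance 4σ² + σ² = 5σ², against σ²/2 for the neighbour average, a tenfold difference. Protocol 11.5 already reports poor signal-to-noise for one-year MRI change. A regression fitted to all patients' pre-randomisation data is therefore preferable to individual extrapolation, and prediction belongs in the sensitivity analysis.
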